### **11. Duration of Therapy and Criteria for Removal from Study**

In the absence of treatment delays due to adverse event(s) greater than 4 weeks from scheduled dose, combination treatment may continue for 2 years with 1 year of ibrutinib monotherapy or until one of the following criteria applies:

- Disease progression,
- Intercurrent illness that prevents further administration of treatment,
- Unacceptable adverse event(s),
- Patient decides to withdraw from the study, or
- General or specific changes in the patient's condition render the patient unacceptable for further treatment in the judgment of the investigator.

#### **11.1. Duration of Follow Up**

The anticipated duration of patients on study will be 3 years. Patients will be followed for 1 year after completion of combination treatment, or for 28 days after removal from study, or until death, whichever occurs first. Patients removed from study for unacceptable adverse events will be followed until resolution or stabilization of the adverse event even if that period is longer than 28 days.

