Study visits and response assessments with IgM measurements will occur day 1 of each cycle through cycle 13 then day of 1 every three cycles after the first year on treatment. Subjects with measurable extramedullary disease will have CT scans every 6 months while on study or until radiographic CR at which point they will occur at the discretion of the investigator. Patients will be considered evaluable for response if they completed the initial 8 weeks of daratumumab induction therapy. Response assessment in Cohort B will be measured from the IgM level recorded prior to ibrutinib initiation. Subjects will continue on combination therapy for 2 years until disease progression or unacceptable toxicities at which point patients will stop daratumumab therapy and come off study. All subjects will be followed for 1 year after completing combination therapy unless they come off study early for other reasons. Subjects achieving a CR will be given an option to continue with single agent commercial ibrutinib or stop all therapy.

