### 9.1. Schedule of Evaluations

Table 1. Schedule of events

Study Procedure	Screening	Cycle -1 Day -28 (Cohort A only prior to daratumumab dosing)	Cycle 1				Cycle 2			
			Week 1	Week 2	Week 3	Week 4	Week 5	Week 6	Week 7	Week 8
			Day 1	Day 8	Day 15	Day 22	Day 1	Day 8	Day 15	Day 22
Daratumumab Administration k			X	X	X	X	X	X	X	X
Informed consent	X									
Demographics	X									
Medical history	X	X	X				X			
Concurrent meds	X	X	X				X			
Physical exam	X	X	X	X	X	X	X	X	X	X
Vital signs, height, weight	X	X	X	X	X	X	X	X	X	X
CBC w/differential	X	X	X	X	X	X	X	X	X	X
Serum chemistry a	X	X	X	X	X	X	X	X	X	X
SIFE+ b	X									
Immunoglobulin M		X	X				X			
Bone marrow biopsy/aspirate c	X									
HIV and Hepatitis Ab screening d	X									
EKG	X									
Pulmonary Function Testing (FEV1 calculation)	X									
Blood Type and Screen	X		X							
Research sample (aspirate) c	X									
Research sample (peripheral blood) j	X									
Adverse event evaluation		Continuously and at each treatment or study visit								
Radiologic evaluation e	X	Radiologic measurements should be performed on Day 1 Cycle 7, 13, 19, 25, 31, 37 day 1 evaluation (+15 day window after Day 1 is allowed)								
B-HCG	X f									

Study Procedure	Cycles 3-6		Cycles 7-13 Day 1	Cycles 14, 15, 17, 18, 20, 21, 23, 24 Day 1 (non- study visits)	Cycles 16, 19, 22 Day 1 (study visits)	Cycles 25, 28, 31, 34 Day 1 (study visits)	EOT Cycle 37 Day 1 visit or 28 days after coming off-study
	Day 1	Day 15					
Daratumumab Administration k	X	X	X	X	X		
Informed consent							
Demographics							
Medical history	X		X	X	X	X	X
Concurrent meds	X		X	X	X	X	X
Physical exam	X		X	X	X	X	X
Vital signs, height, weight	X	X	X	X	X	X	X
CBC w/differential	X	X	X	X	X	X	X
Serum chemistry a	X	X	X	X	X	X	X
SIFE+ b	X g		X h		X	X	
Immunoglobulin M	X	X	X	X			X
Bone marrow biopsy/aspirate c	X i						X i
HIV and Hepatitis Ab screening d	X d		X d		X d	X d	X d
EKG							
Pulmonary Function Testing (FEV1 calculation)							
Blood Type and Screen							
Research sample (aspirate) c	X i						X i
Research sample (peripheral blood) j			X i				X i
Adverse event evaluation	Continuously and at each treatment or study visit						

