Radiologic evaluation e	Radiologic measurements should be performed on Day 1 Cycle 7, 13, 19, 25, 31, 37 day 1 evaluation (+15 day window after Day 1 is allowed)						
B-HCG							

- a. Albumin, alkaline phosphatase, total bilirubin, bicarbonate, BUN, calcium, chloride, creatinine, glucose, LDH, phosphorus, potassium, total protein, SGOT[AST], SGPT[ALT], sodium.
- b. SIFE+ should include serum protein electrophoresis, immunofixation, serum immunoglobulin G, A, M levels, free kappa light chains, free lambda light chains.
- c. Bone marrow biopsy will be performed at baseline and then to confirm complete remission as is standard of care. At baseline, 1 green top tube and 1 lavender top tube will be collected for research.
- d. Hepatitis ab screening should include Hepatitis A IgG with reflex to IgM, Hepatitis B surface Ag, Hepatitis B surface ab, Hepatitis B core ab, Hepatitis C ab. If Hepatitis B surface or core ab, or Hepatitis C ab are positive, reflex testing with PCR for either HBV DNA or HCV RNA should be performed. HBV serology testing does not need to be repeated if performed within three months prior to first dose. Subjects with serologic findings suggestive of HBV vaccination (Anti-HBs positivity as the only serologic marker) and a known history of prior HBV vaccination do not need to be tested for HBV DNA by PCR. Subjects with a history of HBV infection will be monitored for reactivation by HBV DNA by PCR every 3 cycles during treatment (e.g. Cycle 4, 7, 10, etc.), at end of daratumumab treatment (e.g. Cycle 25), and for up to 6 months post-daratumumab therapy (e.g. Cycle 28 and 31).
- e. Radiologic evaluation is defined as CT chest, abdomen and pelvis with contrast. For patients ineligible for contrast CT chest non con with MRI abdomen and pelvis is default.
- f. Serum pregnancy test (women of childbearing potential).
- g. SIFE+ will only be required Cycle 4 D1, the remaining cycles serum IgM will be recorded only.
- h. SIFE+ will only be required for Cycle 7 D1, Cycle 13 D1, the remaining cycles serum IgM will be recorded only.
- i. Research biopsy and aspirate at Cycle 4 Day 1 (+ 15 day window) and then again at progression; 1 green top tube and 1 lavender top tube will be collected.
- j. Peripheral blood samples (2 lavender top tubes) will be collected at screening, Cycles 7, 13, 19, and 25, and at EOT.

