#### **9.3.4. Ibrutinib Monotherapy phase**

The ibrutinib monotherapy phase will occur after patients have completed 24 cycles of combination therapy. After Cycle 24, study visits will still occur every 3 months but no daratumumab infusions will be given. On study visits, the below listed labs and procedures will occur.

Cycles 25, 28, 31, and 34

- Medical history
- Concurrent medications
- Physical exam
- Vital signs (including height and weight)
- CBC with differential
- Serum chemistry (CMP, LDH, phosphorus)
- SIFE+
- Peripheral blood research tube (2 lavender top tubes) (**Cycle 25 only**)
- Adverse event evaluation

- Radiographic evaluation (**Cycle 25 and 31 day 1 only [+ a 15 day window]**)
- HBV DNA PCR if at risk for reactivation (**Cycle 25, 28, and 31 only or every 12 weeks for up to 6 months post-daratumumab therapy**)

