### **10.1. General Concomitant Medication and Supportive Care Guidelines**

Supportive medications in accordance with standard practice (such as for emesis, diarrhea, etc.) are permitted and patient should receive full supportive care during study participation (including fluids and electrolyte replacement, and antibiotics when appropriate). Use of neutrophil growth factors (filgrastim and pegfilgrastim) or red blood cell growth factors (erythropoietin) is permitted per institutional policy. Transfusions may be given in accordance with institutional policy. After consultation with the Sponsor the following may be considered; localized hormonal or bone sparing treatment for non-B-cell malignancies, and localized radiotherapy for medical conditions other than the underlying B-cell malignancies. Short courses ( $\leq 14$  days) of steroid treatment for non-cancer related medical reasons (eg, joint inflammation, asthma exacerbation, rash, antiemetic use and infusion reactions) at doses that do not exceed 100 mg per day of prednisone or equivalent are permitted. Treatment for autoimmune cytopenias are permitted for  $<14$  days at doses that do not exceed 100 mg per day of prednisone or equivalent.

Primary antiviral prophylaxis is permitted as per local standard of care. Per protocol, HBV DNA testing by PCR is mandatory for subjects at risk for HBV reactivation.

For subjects who are diagnosed with HBV reactivation while on treatment, study treatment should be interrupted until the infection is adequately controlled. If the benefits outweigh the risks, study treatment may be resumed with concomitant antiviral prophylaxis as per local standard of care. Consult a liver disease specialist as clinically indicated.

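### The 28-day follow-up limit in Section 11.1 conflicts with HBV DNA testing for up to 6 months after daratumumab, so at-risk subjects removed during combination treatment have no scheduled test after the end-of-treatment visit

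*Combined protocol and SAP*

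**What the plan says.** **Follow-up.** Section 11.1 follows subjects for 1 year after combination treatment, "or for 28 days after removal from study, or until death, whichever occurs first". Its next sentence keeps a subject removed for an unacceptable adverse event under follow-up beyond 28 days, until that event resolves or stabilizes. Section 1 says that on progression or unacceptable toxicity the combination ends, "at which point patients will stop daratumumab therapy and come off study". Section 9.3.5 then gives such a subject one return visit, 28 days later, for EOT procedures.

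**HBV testing.** Footnote d to Table 1 (Section 9.1) states: "Subjects with a history of HBV infection will be monitored for reactivation by HBV DNA by PCR every 3 cycles during treatment". It adds a test at the end of daratumumab and continues "and for up to 6 months post-daratumumab therapy (e.g. Cycle 28 and 31". Section 10.1 says that "HBV DNA testing by PCR is mandatory for subjects at risk for HBV reactivation". Section 9.3.4, the monotherapy-phase list, places the PCR at Cycles 25, 28 and 31, or "every 12 weeks for up to 6 months post-daratumumab therapy". By its own text that phase follows 24 completed cycles of combination therapy.

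**The EOT visit.** Table 1 marks the row "HIV and Hepatitis Ab screening", with footnote d, in the EOT column, which for early leavers is timed at "28 days after coming off-study". The procedure list in Section 9.3.5 does not mention HBV DNA.

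**The concern.** Footnote d covers every subject with a history of HBV infection, whether or not treatment is completed, and it ties the testing period to daratumumab. The visits that would carry out the later tests exist only for subjects who reach monotherapy. A site that follows Section 11.1 closes an early leaver's follow-up after the EOT visit and does not draw the later samples. A site that follows footnote d keeps testing. Nothing in the protocol ranks the two rules.

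The stake is patient safety. Section 7.3, criterion 16, excludes subjects who are positive for hepatitis B surface antigen or HBV DNA, but admits those with resolved infection and a negative PCR. These are the subjects whom footnote d protects. Section 17.3 lists HBV reactivation as an adverse event of special interest, and Section 10.1 says how to manage it. In an early leaver, a reactivation that begins after the EOT visit has no scheduled test to find it.

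**Working it through.** The check is calendar arithmetic; no power or sample-size formula is involved.

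**Inputs.** A cycle is 28 days (Section 12.1). The last daratumumab dose for a completer is Cycle 24 Day 1 (Section 9.3.3). Dosing is weekly in Cycles 1-2, every 2 weeks in Cycles 3-6 and every 4 weeks in Cycles 7-24. The EOT visit is 28 days after removal (Section 9.3.5, Table 1). Section 11 allows an adverse-event delay of at most 4 weeks from the scheduled dose.

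**Step 1: reproduce the plan's window for completers.**
- From Cycle 25 Day 1, Cycle 28 is 3 × 28 = 84 days later and Cycle 31 is 6 × 28 = 168 days later. That is 12 and 24 weeks, which agrees with 12-weekly testing for up to 6 months.
- From the last dose, Cycles 25, 28 and 31 fall on days 28, 112 and 196.

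**Step 2: early leavers.** Let r be the days from the last daratumumab dose to removal. Then EOT day = r + 28. Counted from the last dose, the 12-weekly tests fall on days 84 and 168.

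| Removal during combination treatment | r | EOT day | Day 84 test | Day 168 test |
|---|---|---|---|---|
| On the day of the last dose | 0 | 28 | outside | outside |
| When the next weekly dose is due | 7 | 35 | outside | outside |
| When the next 2-weekly dose is due | 14 | 42 | outside | outside |
| When the next 4-weekly dose is due | 28 | 56 | outside | outside |
| After the longest delay, weekly dosing | 7 + 28 = 35 | 63 | outside | outside |
| After the longest delay, 2-weekly dosing | 14 + 28 = 42 | 70 | outside | outside |
| After the longest delay, 4-weekly dosing | 28 + 28 = 56 | 84 | same day as EOT | outside |

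The last three rows arise from adverse events. If the subject is removed for such an event, the extension in Section 11.1 may keep the subject under follow-up beyond the EOT day shown. It attaches no PCR. The first four rows apply to removal for progression, which has no extension.

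**Step 3: sensitivity to the starting point.** If the 12-week count starts 28 days after the last dose, as Cycle 25 does for completers, the tests move to days 112 and 196. Both then fall after the EOT visit in every row.

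**Step 4: tests before removal.** The on-treatment PCRs at Cycles 4, 7, 10, 13, 16, 19 and 22 are unaffected. A subject removed before Cycle 4 has had none of them; one removed in Cycle 24 can have had all 7.

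**The case against.** The strongest reply is that a specific rule already reaches early leavers. Footnote d gives its cycles only as examples and counts from daratumumab. The 12-weekly alternative in Section 9.3.4 adds nothing for completers, whose Cycles 25, 28 and 31 are already 12 weeks apart, so it may have been written for subjects off that schedule. A mandatory safety rule can reasonably be read to prevail over a general follow-up sentence. This shows the likely intent, and it stands as far as that. But the alternative sits in a list for subjects who have completed combination therapy, and nothing says that it overrides Section 11.1.

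A second reply is that follow-up does continue for some subjects. Section 11.1 extends it for unacceptable adverse events, and Section 20.1 does so for unresolved serious ones. Both follow events already known, and neither schedules a PCR.

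Four stronger readings are tempting, and the documents do not support them:
- *An early leaver has at most one HBV DNA test.* On-treatment tests precede removal, and footnote d asks for an end-of-daratumumab test as well as the one marked at EOT. The gap concerns tests after the EOT visit.
- *A fixed share of a 6-month requirement is lost.* The wording is up to 6 months, which is a ceiling, and intermittent tests do not give continuous coverage.
- *The EOT test itself is missing.* The Study Visit Schedule in Section 9.3 applies the Table 1 procedures at End of Treatment, so its absence from the Section 9.3.5 list is editorial.
- *The safety results are compromised.* The toxicity proportion in Section 16 concerns non-hematologic events of Grade 3 or higher, and the stopping rule in Section 22 uses only the first 8 weeks of combination treatment. Neither depends on these tests.

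**Conclusion.** The conflict is real and is in the current text. For an at-risk subject removed during combination treatment, no PCR is scheduled after the EOT visit, and the 12- and 24-week tests generally fall outside follow-up. The exception in the table is the day-84 test, which can coincide with EOT after the longest delay on 4-weekly dosing.

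The conclusion assumes that a site applies the 28-day limit literally, and that the 12-week count starts at the last dose or up to 28 days after it. It also needs a subject with resolved HBV infection to enrol and leave early. The documents do not give the expected number; with 24 subjects in all it may be very small or zero. Section 10.1 permits antiviral prophylaxis but does not require it. This is a minor patient-safety correction.

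**What to change.** In Section 11.1, state that, unless consent is withdrawn, the 28-day limit does not apply to HBV DNA monitoring. At-risk subjects removed early should continue PCR every 12 weeks (about weeks 12 and 24) until 6 months after the last daratumumab dose. In Section 9.3.5, add HBV DNA PCR for at-risk subjects to the EOT procedures, to match Table 1.

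The cost is a sentence or two in Section 11.1, one line in Section 9.3.5, and up to two blood tests per at-risk early leaver, which footnote d already calls for. The drawback is that some of these patients may have moved to other care, so samples may be harder to obtain.

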### **1.2. Secondary Objectives**

- To assess major response rate with combination daratumumab and ibrutinib cohort A
- To evaluate deepening response rates in Cohort B after daratumumab addition
- To evaluate duration of response (DoR)
- To evaluate time to progression (TTP)
- To assess progression free survival (PFS)
- To assess overall survival (OS)

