#### **9.3.5. End of Treatment or Progression**

Subjects that complete 3 years of therapy will then come off study. At C37D1, subjects will have EOT procedures collected. Additionally any subject that comes off for therapy early for toxicity, or progression will be required to return 28 days later for EOT procedures.

EOT (to be done at Cycle 37 or at time of treatment discontinuation)

- Medical history
- Concurrent medications
- Physical exam
- Vital signs (including height and weight)
- CBC with differential
- Serum chemistry (CMP, LDH, phosphorus)
- Immunoglobulin M
- **Research** bone marrow biopsy/aspirate (at time of progression (1 green top and 1 lavender top))
- Peripheral blood research tubes C37D1 (2 lavender top tubes)
- Adverse event evaluation
- Radiographic evaluation (**Cycle 31 day 1 only [+ a 15 day window]**)

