### **14.1. Response Criteria**

Subjects will be evaluable for a response if they have completed 2 Cycles of combination induction treatment (Weeks 1-8). See **Appendix C** for summary of response criteria.

**Complete Response (CR):** A complete response (CR) is defined as having resolution of WM related symptoms, normalization of serum IgM levels with complete disappearance of IgM paraprotein by immunofixation, and resolution of any adenopathy or splenomegaly. A complete response requires reconfirmation demonstrating normal serum IgM levels, and absence of IgM paraprotein by immunofixation by a measurement repeated at least 2 weeks later.

**Very Good Partial Response (VGPR):**  $\geq 90\%$  reduction in serum IgM levels, or normalization of serum IgM levels.

**Partial Response (PR):**  $\geq 50\%$  reduction in serum IgM levels

**Minor Response (MR):** 25-49% reduction in serum IgM levels

**Progressive Disease (PD):** >25% increase in serum IgM level occurs with an absolute increase of at least 500mg/dL from the lowest attained response value, or progression of clinically significant disease related symptoms. Reconfirmation of the initial IgM increase is required when the IgM is the sole criterion for progressive disease. For participants on active therapy who are on a drug hold for > 7 days an increase in serum IgM will not be considered progression if in the investigators opinion it is secondary to the drug hold. Subjects will be allowed reinitiation of drug. If after four consecutive weeks on active therapy there is no decrease in IgM, subjects will be considered to have progressive disease. If there is clinical benefit continuation on trial will be considered. Cases such as this should be discussed with the study sponsor. An increase of 1cm in any axis for adenopathy or 2 cm in the craniocaudal axis of the spleen will be considered progression. Development of central nervous system or transformation will be considered progressive events.

**Stable Disease (SD):** <25% change in serum IgM levels in the absence of new or increasing adenopathy, splenomegaly or other signs of active WM.

**Overall Response:** Includes MR, PR, VGPR, CR

**Major Response:** Includes PR, VGPR, CR

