#### 14.2. Time to Event Definitions

**Duration of Response (DoR):** The duration of overall response is measured from the time measurement criteria are met for Minor response or better until the first date that recurrent or progressive disease is objectively documented (taking as reference for progressive disease the smallest IgM measurements recorded since the treatment started).

**Progression-Free Survival (PFS):** PFS is defined as the duration of time from start of treatment to time of progression or death.

**Overall Survival (OS):** OS is defined as the duration of time from start of treatment to time of death or last follow-up.

**Time to Progression (TTP):** TTP is defined as the time to tumor progression as defined in Section 9.1. If the subject has not progressed, then data will be censored at the last study visit at which a tumor assessment was performed.

**Evaluation of toxicity.** All patients will be evaluable for toxicity from the time of their first treatment with Daratumumab.

**Evaluation of response.** All patients included in the study will be assessed for response to treatment if they have completed Cycle 2.

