## **16. Statistical Considerations**

Because this is a pilot study, no formal sample size/power calculation is required. However, with 12 patients each cohort, an exact binomial (Clopper-Pearson) 95% confidence interval for the toxicity proportion (i.e., primary endpoint) can be constructed to have a width of approximately 45.0% (1.6%, 46.5%) (i.e., separate confidence interval for each cohort). This calculation assumes that the toxicity proportion for the incidence of non-hematologic Grade  $\geq 3$  events will be no greater than 15% in either cohort. Secondary endpoints include major response (PR/VGPR/CR), percentage of patients with deepening of response in Cohort B, duration of response, and time to progression. Given this is a pilot study with low subject enrollment and lack of power, analysis of outcomes will remain descriptive without comparison analyses between cohorts. The toxicity and major response proportions will be calculated for each cohort along with exact binomial (Clopper-Pearson) 95% confidence intervals. Duration of response and time to progression will be descriptively reported for each cohort. Assuming adequate follow-up time, Kaplan-Meier survival analysis will be used to assess progression-free survival (PFS) and overall survival (OS) in each cohort. All p-values will be two-sided with statistical significance evaluated at the 0.05 alpha level. Ninety-five percent confidence intervals for 1) the toxicity proportion, 2) the major response proportion, and 3) median PFS/OS-time and PFS/OS proportions, will be calculated to assess the precision of the obtained estimates. All analyses will

be performed in SAS Version 9.4 (SAS Institute, Inc., Cary, NC) and Stata Version 15.0 (StataCorp, College Station, TX).

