#### **17.4. Adverse Events of Special Interest for Ibrutinib (Imbruvica®)**

Adverse events of special interest are events that Janssen Scientific Affairs, LLC is actively monitoring as a result of a previously identified signal (even if non-serious). These adverse events are:

- *Major Hemorrhage*

Major hemorrhage is defined as any hemorrhagic event that is Grade 3 or greater in severity or that results in 1 of the following: intraocular bleeding causing loss of vision, the need for a transfusion of 2 or more units of red cells or an equivalent amount of whole blood, hospitalization, or prolongation of hospitalization.

- *Intracranial Hemorrhage*

Any intracranial hemorrhage adverse event, including subdural hematoma/hemorrhage, epidural hematoma/hemorrhage and intracerebral hemorrhage, of any grade severity, will be captured as an event of special interest.

- *Other Malignancies*

In addition to all routine AE reporting, all new malignant tumors, including solid tumors, skin malignancies and hematologic malignancies, are to be reported for the duration of study treatment and during any protocol-specified follow-up periods including post-progression follow-up for overall survival.

Any Adverse Event of Special Interest that is to be reported to the COMPANY should be recorded on a Serious Adverse Event Report Form and be reported to the COMPANY **within 24 hours of knowledge of the event.**

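### Overall survival is to be estimated by Kaplan-Meier, but patients who progress are followed for only 28 days, which biases the curve upward if progression raises the risk of death

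*Combined protocol and SAP*

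**What the plan says.** OS is a secondary objective in the Synopsis and in Section 1.2. Section 16 states that "Kaplan-Meier survival analysis will be used to assess progression-free survival (PFS) and overall survival (OS) in each cohort", subject to follow-up being adequate (a term it does not define), with 95% confidence intervals for the medians and for the survival proportions.

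The rules for follow-up are these:

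- Section 1: patients stay on combination therapy until progression or unacceptable toxicity, "at which point patients will stop daratumumab therapy and come off study". Section 11 also lists progression as a reason to end treatment.
- Section 11.1: follow-up runs for one year after combination treatment, or "for 28 days after removal from study, or until death, whichever occurs first".
- Section 9.3.5: a patient who "comes off for therapy early for toxicity, or progression will be required to return 28 days later for EOT procedures". The schedule in Table 1 has no survival contact after that visit.
- Section 14.2: "OS is defined as the duration of time from start of treatment to time of death or last follow-up". It gives no further censoring rule for OS.

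Two passages point the other way. Section 17.4 asks for new malignancies to be reported "during any protocol-specified follow-up periods including post-progression follow-up for overall survival". Section 14.1 says of some patients whose IgM indicates progression: "If there is clinical benefit continuation on trial will be considered".

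**The concern.** Kaplan-Meier treats a censored patient as having the same future risk of death as those still under observation. Here the censoring is triggered by progression. Unless progression leaves the death hazard unchanged, the patients removed are at higher risk than those who remain. The later part of the curve is then estimated mainly from patients who have not progressed.

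The estimate would be closer to survival while on study than to overall survival. The rationale in Section 3 looks for better durability than ibrutinib alone has shown, and Section 6.1.5 reports OS for ibrutinib alone. A reader could set the trial's OS beside those figures without knowing that deaths after progression were mostly not collected.

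**Working it through.** The plan states no event count or precision for OS, so there is no OS figure to reproduce. The check asks how large the bias could be.

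**Inputs**

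- Section 6.1.5, the 63-patient phase II study: 24-month PFS 69.1%, OS 95.2%.
- Section 6.1.5, the 31-patient ibrutinib-only arm: 18-month PFS 86%, OS 97%.
- Censoring 28 days after progression (Sections 9.3.5 and 11.1).
- Horizon: Cycle 37 Day 1 is 36 × 28 = 1008 days, or 2.76 years, from Cycle 1 Day 1.
- 12 patients per cohort (Section 16).
- Assumption: R, the ratio of the death hazard after progression to that before it. The documents do not give it. It is varied from 1 to 10 with no preferred value.
- Assumptions: constant hazards, and every patient who progresses is censored at 28 days.

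**Model**

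- Hazard of progression or death: λ = −ln(PFS)/t. Phase II study: −ln(0.691)/2 = 0.1848 per year. Ibrutinib-only arm: −ln(0.86)/1.5 = 0.1005 per year.
- Death hazard h before progression and R·h after it; progression hazard p = λ − h.
- True OS(t) = exp(−λt) + p·exp(−Rht)·[1 − exp(−(λ − Rh)t)]/(λ − Rh). For each R, h is solved so that OS equals the reported value at the reported time.
- The Kaplan-Meier limit accumulates the death hazard among those still observed: patients free of progression plus those within 28 days after it.

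**One case in full (phase II calibration, R = 5)**

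h = 0.0155, R·h = 0.0775, p = 0.1848 − 0.0155 = 0.1693, λ − R·h = 0.1073.

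- True OS at Cycle 37: 0.6005 + 0.1693 × 0.8074 × 0.2563/0.1073 = 0.6005 + 0.3265 = 0.927.
- If patients were censored at the moment of progression, Kaplan-Meier would tend to exp(−0.0155 × 2.76) = 0.958. The 28-day window lowers this to 0.956.
- Bias: 95.6 − 92.7 = 2.9 points.

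A simulation of 2 million patients gives the same 0.927 and 0.956.

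**Results, phase II calibration** (true OS / Kaplan-Meier, %)

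| R | h per year | 24 months | Bias, points | Cycle 37 | Bias, points | Deaths captured by Cycle 37 |
|---|---|---|---|---|---|---|
| 1 | 0.0246 | 95.2 / 95.2 | 0 | 93.4 / 93.4 | 0 | 82% |
| 2 | 0.0215 | 95.2 / 95.7 | 0.5 | 93.2 / 94.2 | 1.0 | 70% |
| 3 | 0.0190 | 95.2 / 96.2 | 1.0 | 93.0 / 94.8 | 1.8 | 61% |
| 5 | 0.0155 | 95.2 / 96.8 | 1.6 | 92.7 / 95.6 | 2.9 | 49% |
| 10 | 0.0105 | 95.2 / 97.7 | 2.5 | 92.3 / 96.8 | 4.5 | 34% |

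**Results, ibrutinib-only arm calibration.** For R from 2 to 10 the bias is 0.1 to 0.9 points at 18 months, 0.3 to 1.6 at 24 months and 0.5 to 3.0 at Cycle 37. Between 83% and 50% of deaths are captured by Cycle 37.

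**Scale for one cohort of 12**

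- Expected progressions by Cycle 37: 12 × (p/λ) × [1 − exp(−λt)]. For R = 5 this is 12 × 0.916 × 0.3995 = 4.4. The range over R is 4.2 to 4.5 (phase II calibration) or 2.3 to 2.5 (ibrutinib-only arm).
- Standard error: √[S(1 − S)/12]. For S = 0.927 this is √(0.927 × 0.073/12) = 7.5 points. Over both calibrations it is about 6 points at 24 months and 6.6 to 7.7 at Cycle 37, above the bias in every case.
- Chance of no death in a cohort by Cycle 37 (phase II calibration, R = 5): 0.927^12 = 40% with full vital status. As recorded, the death probability is 0.49 × 0.073 = 0.036, and 0.964^12 is about 65%.

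**The case against.** The strongest reply has five parts.

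- **Section 16 makes the analysis conditional on adequate follow-up.** It does, but it defines no standard and adds no contact after removal. Longer follow-up of those who remain does not remove censoring that depends on progression.
- **The documents do not settle that follow-up stops at 28 days.** Section 17.4 presupposes survival follow-up after progression, and nothing forbids collecting later vital status. That stands as a contradiction to reconcile. Section 17.4 is a safety-reporting clause, however, and sets no schedule, interval or duration; the sections that govern follow-up stop at 28 days.
- **Some patients with IgM progression may stay on trial.** This is true, case by case and only with clinical benefit, and it would lessen the bias. Those kept are selected for doing well.
- **The horizon is itself uncertain.** The Synopsis runs to Cycle 52 (four years), while Sections 9.3.5 and 11.1 stop at three. At Cycle 52 Day 1 (51 × 28 = 1428 days) the phase II calibration gives about 1.9 to 8.2 points for R from 2 to 10. The point becomes larger, but the bias at R = 10 is still below the standard error of about 9.6 points (√(0.873 × 0.127/12)).
- **The consequence is small.** This is fair. At R = 1 the bias is zero, fewer than one death per cohort is expected by Cycle 37, and the plan makes no formal comparison with historical OS. The share of deaths captured is also not a measure of bias, since it is 82% when the bias is zero.

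The 28-day limit also covers removal for other reasons. Patients removed for an adverse event may be followed longer, but only for that event. The gap is therefore somewhat wider than progression alone.

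**Conclusion.** The concern holds, as a minor point. As written, the plan censors OS about 28 days after progression, and the Kaplan-Meier curve is too high whenever progression raises the risk of death. At Cycle 37 the bias is 1.0 to 4.5 points under the phase II calibration and 0.5 to 3.0 under the other, for hazard ratios of 2 to 10; it is zero at a ratio of 1. These figures rest on constant hazards, on historical ibrutinib results carried over to this trial, and on a hazard ratio that the documents do not supply. With 12 patients per cohort, sampling error exceeds the bias in every case examined. Unlike sampling error, though, the bias has a known direction under that condition and would not shrink with more patients. OS is descriptive, no test or decision depends on it, and the primary safety endpoint is unaffected.

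**What to change.** In Section 11.1, add collection of vital status by chart review or telephone for every treated patient, to one common cut-off date and whatever the reason for leaving treatment, unless consent to follow-up is withdrawn. In Section 14.2, state that OS is censored at the date last known alive. Reconcile Sections 9.3.5, 11.1 and 17.4 so that the survival follow-up named in Section 17.4 exists, and settle whether the study horizon is Cycle 37 or Cycle 52.

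The cost is about one protocol paragraph, matching consent wording, and occasional chart checks or calls for at most 24 patients. No visits or procedures are added.

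If this follow-up is not wanted, label the result on-study survival, or remove OS from the Synopsis and Sections 1.2, 14.2 and 16. That needs only a text edit but gives up the endpoint.
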